### **7.2.1 Definition of an Overdose for This Protocol and Reporting of Overdose to the Sponsor and to Merck**

For purposes of this study, an overdose of pembrolizumab will be defined as any dose of 1,000 mg or greater ( $\geq 5$  times the indicated dose). No specific information is available on the treatment of overdose of pembrolizumab. In the event of overdose, the participant should be observed closely for signs of toxicity. Appropriate supportive treatment should be provided if clinically indicated.

If an adverse event(s) is associated with (“results from”) the overdose of a Merck product, the adverse event(s) is reported as a serious adverse event, even if no other seriousness criteria are met.

If a dose of Merck’s product meeting the protocol definition of overdose is taken without any associated clinical symptoms or abnormal laboratory results, the overdose is reported as a

non-serious Event of Clinical Interest (ECI), using the terminology “accidental or intentional overdose without adverse effect.”

All reports of overdose with and without an adverse event must be reported within 24 hours to the Sponsor and within 2 working days hours to Merck Global Safety. (Attn: Worldwide Product Safety; [contact])

### **7.2.2 Reporting of Pregnancy and Lactation to the Sponsor and to Merck**

Although pregnancy and infant exposure during breast feeding are not considered adverse events, it is the responsibility of investigators or their designees to report any pregnancy or lactation in a participant (spontaneously reported to them) that occurs during the study.

Pregnancies and infant exposures during breastfeeding that occur after the consent form is signed but before treatment allocation/randomization must be reported by the investigator if they cause the participant to be excluded from the trial, or are the result of a protocol-specified intervention, including but not limited to washout or discontinuation of usual therapy, diet, placebo treatment or a procedure.

Pregnancies and infant exposures during breastfeeding that occur from the time of treatment allocation/randomization through 120 days following cessation of pembrolizumab (pembroRT cohort) or 180 days following cessation of chemotherapy (chemoRT cohort) or 30 days following cessation of treatment if the participant initiates new anticancer therapy, whichever is earlier, must be reported by the investigator. All reported pregnancies must be followed to the completion/termination of the pregnancy. Pregnancy outcomes of spontaneous abortion, missed abortion, benign hydatidiform mole, blighted ovum, fetal death, intrauterine death, miscarriage and stillbirth must be reported as serious events (Important Medical Events). If the pregnancy continues to term, the outcome (health of infant) must also be reported.

Such events must be reported within 24 hours to the Sponsor and within 2 working days to Merck Global Safety. (Attn: Worldwide Product Safety; [contact])

### **7.2.3 Immediate Reporting of Adverse Events to the Sponsor and to Merck**

#### **7.2.3.1 Serious Adverse Events**

A serious adverse event is any adverse event occurring at any dose or during any use of Merck's product that:

- Results in death;
- Is life threatening;
- Results in persistent or significant disability/incapacity;
- Results in or prolongs an existing inpatient hospitalization;
- Is a congenital anomaly/birth defect;
- Is another important medical event

• **Note:** In addition to the above criteria, adverse events meeting either of the below criteria, although not serious per ICH definition, are reportable to the Merck in the

same timeframe as SAEs to meet certain local requirements. Therefore, these events are considered serious by Merck for collection purposes.

- Is a new cancer (that is not a condition of the study);
- Is associated with an overdose.

Refer to Table 7 for additional details regarding each of the above criteria.

For the time period beginning when the consent form is signed until treatment allocation/randomization, any serious adverse event, or follow up to a serious adverse event, including death due to any cause that occurs to any participant must be reported within 24 hours to the Sponsor and within 2 working days to Merck Global Safety if it causes the participant to be excluded from the trial, or is the result of a protocol-specified intervention, including but not limited to washout or discontinuation of usual therapy, diet, placebo treatment or a procedure.

For the time period beginning at treatment allocation through 90 days following cessation of treatment, or 30 days following cessation of treatment if the participant initiates new anticancer therapy, whichever is earlier, any serious adverse event, or follow up to a serious adverse event, including death due to any cause whether or not related to the Merck product, must be reported within 24 hours to the Sponsor and within 2 working days to Merck Global Safety.

Additionally, any serious adverse event, considered by an investigator who is a qualified physician to be related to Merck product that is brought to the attention of the investigator at any time following consent through the end of the specified safety follow-up period specified in the paragraph above, or at any time outside of the time period specified in the previous paragraph also must be reported immediately to Merck Global Safety.

All participants with serious adverse events must be followed up for outcome.

**SAE reports and any other relevant safety information are to be forwarded to the Merck Global Safety [contact]**

**SAE reports and any other relevant safety information are to be forwarded to Principal Investigator ([name]., [[contact]](mailto:[contact])) as well as the study sponsor's Data Safety Monitoring Committee ([[contact]](mailto:[contact])).**

A copy of all 15 Day Reports and Annual Progress Reports is submitted as required by FDA, European Union (EU), Pharmaceutical and Medical Devices agency (PMDA) or other local regulators. Investigators will cross reference this submission according to local regulations to the Merck Investigational Compound Number (IND, CSA, etc.) at the time of submission. Additionally, investigators will submit a copy of these reports to Merck & Co., Inc. (Attn: Worldwide Product Safety; [contact]) at the time of submission to FDA.

### 7.2.3.2 Events of Clinical Interest

Selected non-serious and serious adverse events are also known as Events of Clinical Interest (ECI) and must be reported within 2 working days to Merck Global Safety. (Attn: Worldwide Product Safety; [contact]).

For the time period beginning when the consent form is signed until treatment allocation/randomization, any ECI, or follow up to an ECI, that occurs to any participant must be reported within 2 working days to Merck Global Safety if it causes the participant to be excluded from the trial, or is the result of a protocol-specified intervention, including but not limited to washout or discontinuation of usual therapy, diet, placebo treatment or a procedure.

For the time period beginning at treatment allocation through 90 days following cessation of treatment, or 30 days following cessation of treatment if the participant initiates new anticancer therapy, whichever is earlier, any ECI, or follow up to an ECI, whether or not related to Merck product, must be reported within 2 working days to Merck Global Safety.

Events of clinical interest for this trial include:

1. an overdose of Merck product, as defined in Section 7.2.1 - Definition of an Overdose for This Protocol and Reporting of Overdose to the Sponsor, that is not associated with clinical symptoms or abnormal laboratory results.
2. an elevated AST or ALT lab value that is greater than or equal to 3X the upper limit of normal and an elevated total bilirubin lab value that is greater than or equal to 2X the upper limit of normal and, at the same time, an alkaline phosphatase lab value that is less than 2X the upper limit of normal, as determined by way of protocol-specified laboratory testing or unscheduled laboratory testing.\*

\*Note: These criteria are based upon available regulatory guidance documents. The purpose of the criteria is to specify a threshold of abnormal hepatic tests that may require an additional evaluation for an underlying etiology.

### 7.2.4 Evaluating Adverse Events

An investigator who is a qualified physician will evaluate all adverse events according to the NCI Common Terminology for Adverse Events (CTCAE), version 4.0. Any adverse event which changes CTCAE grade over the course of a given episode will have each change of grade recorded on the adverse event case report forms/worksheets.

All adverse events regardless of CTCAE grade must also be evaluated for seriousness.

Table 7 Evaluating Adverse Events

An investigator who is a qualified physician, will evaluate all adverse events as to:

V4.0 CTCAE Grading	Grade 1	Mild; asymptomatic or mild symptoms; clinical or diagnostic observations only; intervention not indicated.
	Grade 2	Moderate; minimal, local or noninvasive intervention indicated; limiting age-appropriate instrumental ADL.
	Grade 3	Severe or medically significant but not immediately life-threatening; hospitalization or prolongation of hospitalization indicated; disabling; limiting self-care ADL.
	Grade 4	Life threatening consequences; urgent intervention indicated.
	Grade 5	Death related to AE
Seriousness	A serious adverse event is any adverse event occurring at any dose or during any use of Merck product that:	
	† Results in death ; or	
	† Is life threatening ; or places the participant, in the view of the investigator, at immediate risk of death from the event as it occurred (Note: This does not include an adverse event that, had it occurred in a more severe form, might have caused death.); or	
	† Results in a persistent or significant disability/incapacity (substantial disruption of one's ability to conduct normal life functions); or	
	† Results in or prolongs an existing inpatient hospitalization (hospitalization is defined as an inpatient admission, regardless of length of stay, even if the hospitalization is a precautionary measure for continued observation. (Note: Hospitalization for an elective procedure to treat a pre-existing condition that has not worsened is not a serious adverse event. A pre-existing condition is a clinical condition that is diagnosed prior to the use of a Merck product and is documented in the patient's medical history.); or	
	† Is a congenital anomaly/birth defect (in offspring of participant taking the product regardless of time to diagnosis); or	
	Is a new cancer (that is not a condition of the study) (although not serious per ICH definition, is reportable to the Sponsor within 24 hours and to Merck within 2 working days to meet certain local requirements); or	
	Is an overdose (whether accidental or intentional). Any adverse event associated with an overdose is considered a serious adverse event for collection purposes. An overdose that is not associated with an adverse event is considered a non-serious event of clinical interest and must be reported within 24 hours to the Sponsor and to Merck within 2 working days.	
	Other important medical events that may not result in death, not be life threatening, or not require hospitalization may be considered a serious adverse event when, based upon appropriate medical judgment, the event may jeopardize the participant and may require medical or surgical intervention to prevent one of the outcomes	

	listed previously (designated above by a †).						
Duration	Record the start and stop dates of the adverse event. If less than 1 day, indicate the appropriate length of time and units						
Action taken	Did the adverse event cause Merck product to be discontinued?						
Relationship to Merck Product	
Did Merck product cause the adverse event? The determination of the likelihood that Merck product caused the adverse event will be provided by an investigator who is a qualified physician. The investigator's signed/dated initials on the source document or worksheet that supports the causality noted on the AE form, ensures that a medically qualified assessment of causality was done. This initialed document must be retained for the required regulatory time frame. The criteria below are intended as reference guidelines to assist the investigator in assessing the likelihood of a relationship between the test drug and the adverse event based upon the available information.
 
The following components are to be used to assess the relationship between Merck product and the AE; the greater the correlation with the components and their respective elements (in number and/or intensity), the more likely Merck product caused the adverse event (AE):
 
 
 Exposure	Is there evidence that the participant was actually exposed to Merck product such as: reliable history, acceptable compliance assessment (pill count, diary, etc.), expected pharmacologic effect, or measurement of drug/metabolite in bodily specimen?	
 
 Time Course	Did the AE follow in a reasonable temporal sequence from administration of Merck product? Is the time of onset of the AE compatible with a drug-induced effect (applies to trials with investigational medicinal product)?	
 
 Likely Cause	Is the AE not reasonably explained by another etiology such as underlying disease, other drug(s)/vaccine(s), or other host or environmental factors	
 
	Exposure	Is there evidence that the participant was actually exposed to Merck product such as: reliable history, acceptable compliance assessment (pill count, diary, etc.), expected pharmacologic effect, or measurement of drug/metabolite in bodily specimen?	Time Course	Did the AE follow in a reasonable temporal sequence from administration of Merck product? Is the time of onset of the AE compatible with a drug-induced effect (applies to trials with investigational medicinal product)?	Likely Cause	Is the AE not reasonably explained by another etiology such as underlying disease, other drug(s)/vaccine(s), or other host or environmental factors
Exposure	Is there evidence that the participant was actually exposed to Merck product such as: reliable history, acceptable compliance assessment (pill count, diary, etc.), expected pharmacologic effect, or measurement of drug/metabolite in bodily specimen?						
Time Course	Did the AE follow in a reasonable temporal sequence from administration of Merck product? Is the time of onset of the AE compatible with a drug-induced effect (applies to trials with investigational medicinal product)?						
Likely Cause	Is the AE not reasonably explained by another etiology such as underlying disease, other drug(s)/vaccine(s), or other host or environmental factors						

Relationship to Merck Product (continued)	The following components are to be used to assess the relationship between the test drug and the AE: (continued)	
	Dechallenge	
Was Merck product discontinued or dose/exposure/frequency reduced?
 
If yes, did the AE resolve or improve?
 
If yes, this is a positive dechallenge. If no, this is a negative dechallenge.
 
(Note: This criterion is not applicable if: (1) the AE resulted in death or permanent disability; (2) the AE resolved/improved despite continuation of the Sponsor's product; or (3) the trial is a single-dose drug trial); or (4) Sponsor's product(s) is/are only used one time.)

	Rechallenge	
Was the participant re-exposed to Merck product in this study?
 
If yes, did the AE recur or worsen?
 
If yes, this is a positive rechallenge. If no, this is a negative rechallenge.
 
(Note: This criterion is not applicable if: (1) the initial AE resulted in death or permanent disability, or (2) the trial is a single-dose drug trial); or (3) Sponsor's product(s) is/are used only one time).
 
NOTE: IF A RECHALLENGE IS PLANNED FOR AN ADVERSE EVENT WHICH WAS SERIOUS AND WHICH MAY HAVE BEEN CAUSED BY MERCK PRODUCT, OR IF REEXPOSURE TO MERCK PRODUCT POSES ADDITIONAL POTENTIAL SIGNIFICANT RISK TO THE PARTICIPANT, THEN THE RECHALLENGE MUST BE APPROVED IN ADVANCE BY THE SPONSOR AS PER DOSE MODIFICATION GUIDELINES IN THE PROTOCOL.

	Consistency with Trial Treatment Profile	Is the clinical/pathological presentation of the AE consistent with previous knowledge regarding Merck product or drug class pharmacology or toxicology?
The assessment of relationship will be reported on the case report forms /worksheets by an investigator who is a qualified physician according to his/her best clinical judgment, including consideration of the above elements.		
Record one of the following		Use the following scale of criteria as guidance (not all criteria must be present to be indicative of Merck product relationship).
Yes, there is a reasonable possibility of Merck product relationship.		There is evidence of exposure to Merck product. The temporal sequence of the AE onset relative to the administration of Merck product is reasonable. The AE is more likely explained by Merck product than by another cause.
No, there is not a reasonable possibility of Merck product relationship		Participant did not receive the Merck product OR temporal sequence of the AE onset relative to administration of Merck product is not reasonable OR the AE is more likely explained by another cause than the Merck product. (Also entered for a participant with overdose without an associated AE.)

### 7.2.5 Sponsor Responsibility for Reporting Adverse Events

All Adverse Events will be reported to regulatory authorities, IRB/IECs and investigators in accordance with all applicable global laws and regulations.

## 8.0 STATISTICAL ANALYSIS PLAN

### 8.1 Statistical Analysis Plan – Primary Endpoint and Sample Size Calculation

The **primary endpoint** is progression-free survival (PFS) in the PembroRT cohort one year following study enrollment. PFS duration will be defined as the time from study registration to the date of disease progression or death from any cause. In cases where a scan is concerning for progressive disease based on RECIST 1.1 criteria, and progression is confirmed on a subsequent scan 4-8 weeks later (satisfying iRECIST criteria for progression), the date of disease progression would be the date of the first scan demonstrating progression. PFS rates will be estimated using the Kaplan-Meier Survival method, from which the probability of PFS at various time points and corresponding 95% confidence intervals will be estimated. If a patient is lost to follow-up without having disease progression, progression-free survival will be censored at the date of the patient's last clinic visit. Based on published multi-institutional trials and data from our institution, we expect the one-year progression-free survival rate ( $H_0$ ) to be to 40% with standard chemoradiotherapy. We hypothesize that this rate will be at least 65% ( $H_1$ ) for subjects in the PembroRT cohort. A one sample two-sided log-rank test will be used to compare the one-year PFS rate in the PembroRT cohort against the expected rate with ChemoRT. We plan to accrue **25 subjects to the PembroRT cohort**. Assuming that the accrual period will last 18 months and that event rates will follow an exponential distribution, this sample size will provide 81% power to detect an improvement in PFS at 1 year at a 5% level of significance using a one sample two-sided log-rank test [48, 49].

The ChemoRT cohort will be open to accrual while accrual to the PembroRT cohort is ongoing. We expect that approximately 40% of patients with locally advanced NSCLC have PD-L1 expression of at least 50%. We therefore expect that approximately 38 subjects will be enrolled and treated with standard concurrent chemoradiotherapy as part of this trial, which will yield a **total sample size of approximately 63 subjects**.

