#### **7.1.2.6.2 End of Treatment and Follow-up Tumor Imaging**

In participants who discontinue study treatment, tumor imaging should be performed at the time of treatment discontinuation ( $\pm 4$ -week window). If previous imaging was obtained within 4 weeks prior to the date of discontinuation, then imaging at treatment discontinuation is not mandatory. In participants who discontinue study treatment due to documented disease progression and the Investigator elects not to implement iRECIST, this is the final required tumor imaging.

In participants who discontinue study treatment without documented disease progression, every effort should be made to continue monitoring their disease status by tumor imaging using the same imaging schedule used while on treatment.

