#### **7.1.2.6.3 RECIST 1.1 Assessment of Disease**

RECIST 1.1 will be used as the primary measure for assessment of tumor response, date of disease progression, and as a basis for all protocol guidelines related to disease status (e.g., discontinuation of study treatment). Although RECIST 1.1 references a maximum of 5 target lesions in total and 2 per organ, the Sponsor allows a maximum of 10 target lesions in total and 5 per organ, if clinically relevant to enable a broader sampling of tumor burden.

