#### **7.1.2.6.4 iRECIST Assessment of Disease**

iRECIST is based on RECIST 1.1, but adapted to account for the unique tumor response seen with immunotherapeutic drugs. When clinically stable, participants should not be discontinued until progression is confirmed by the Investigator, working with local radiology, according to the rules below. This allowance to continue treatment despite initial radiologic PD takes into account the observation that some participants can have a transient tumor flare in the first few months after the start of immunotherapy, and then experience subsequent disease response.

[figure not shown]
A description of the adaptations and iRECIST process is provided in the Appendix, with additional detail in the iRECIST publication[47]. iRECIST will be used by the Investigator to assess tumor response and progression, and make treatment decisions.

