#### Persistent iUPD

Progression is considered not confirmed, and the overall response remains iUPD, if:

- None of the progression-confirming factors identified above occurs AND
- The target lesion sum of diameters (initial target lesions) remains above the initial PD threshold (by RECIST 1.1)

Additional imaging for confirmation should be scheduled 4 to 8 weeks from the scan on which iUPD is seen. This may correspond to the next visit in the original visit schedule. The

assessment of the subsequent confirmation scan proceeds in an identical manner, with possible outcomes of iCPD, iUPD, and iSD/iPR/iCR.

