#### *Resolution of iUPD*

Progression is considered not confirmed, and the overall response becomes iSD/iPR/iCR, if:

- None of the progression-confirming factors identified above occurs, AND
- The target lesion sum of diameters (initial target lesions) is not above the initial PD threshold.

The response is classified as iSD or iPR (depending on the sum of diameters of the target lesions), or iCR if all lesions resolve.

In this case, the initial iUPD is considered to be pseudo-progression, and the level of suspicion for progression is “reset”. This means that the next visit that shows radiographic progression, whenever it occurs, is again classified as iUPD by iRECIST, and the confirmation process is repeated before a response of iCPD can be assigned.

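### Section 8.1 does not settle whether a RECIST 1.1 progression that later resolves under iRECIST is a primary PFS event; censoring at the last clinic visit is a smaller, separate weakness

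*Combined protocol and SAP*

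**What the plan says.** Section 8.1 measures PFS from registration to progression or death, without naming a criterion in that sentence. It then dates one case: a scan that raises concern under RECIST 1.1, where "progression is confirmed on a subsequent scan 4-8 weeks later (satisfying iRECIST criteria for progression"), is dated at the first of the two scans. Patients lost without progression are censored at their last clinic visit.

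Section 7.1.2.6.3 attaches no confirmation condition: "RECIST 1.1 will be used as the primary measure for assessment of tumor response, date of disease progression". Section 7.1.2.6.4 gives the other system a role too: "iRECIST will be used by the Investigator to assess tumor response and progression, and make treatment decisions".

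Appendix 4 describes two outcomes of a rescan that does not confirm progression:

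- **Resolution.** "the initial iUPD is considered to be pseudo-progression", and "the next visit that shows radiographic progression, whenever it occurs, is again classified as iUPD by iRECIST". iUPD is unconfirmed progressive disease.
- **Persistence.** "Progression is considered not confirmed, and the overall response remains iUPD". A further scan follows: "Additional imaging for confirmation should be scheduled 4 to 8 weeks from the scan on which iUPD is seen".

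The trial is open-label (section 9.3), and progression is assessed by the investigator (section 7.1.2.6.1, Tumor Imaging During the Study, and section 7.1.2.6.4).

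**The concern.** Take a patient whose scan meets RECIST 1.1 progression and whose rescan shows stable or responding disease. Section 7.1.2.6.3, read literally, makes the first scan a PFS event. Section 8.1 dates only confirmed progression, and Appendix 4 sets the initial progression aside. Read together, they leave the patient event-free until a later progression or death. No passage says which reading governs the primary endpoint.

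Two analysts could therefore code the same patient differently in a 25-patient single-arm test, and in an open-label trial the choice could be made with the results in view. The comparator is a fixed 40%, so the event must be defined as it was for that figure, and section 8.1 does not state that definition.

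The censoring rule is a separate matter. A clinic visit without imaging does not show that the patient is progression-free, so the rule credits unassessed time.

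**Working it through.** **1. Inputs.** From section 8.1: n = 25, one-year PFS 40% against 65%, 18 months' accrual, exponential times, two-sided 5% one-sample log-rank test, stated power 81%. Assumed: uniform accrual and analysis 12 months after the last enrolment, so follow-up runs from 1.0 to 2.5 years.

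- Null hazard: -ln 0.40 = 0.916 per year.
- Alternative hazard: -ln 0.65 = 0.431 per year (ratio 0.470).
- Classical statistic: Z = (O - E)/√E.
- Averaged-variance statistic: Z = (O - E)/√((O + E)/2).
- E = 0.916 × total follow-up time in years. A favourable result is Z < -1.96, nominally 2.5%.

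**2. The plan's power.** Under the alternative, expected O = 25 × [1 - (e^-0.431 - e^-1.077)/(0.431 × 1.5)] = 13.03 and expected E = 13.03/0.470 = 27.72. The simulated variance of O - E is 25.57. Power = Φ[(14.69 - 1.96 × √27.72)/√25.57] = Φ(0.86) = 80.6%, which matches 81%. Direct simulation of the classical test gives about 83%. The sample size is not in question.

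**3. The two readings side by side.**

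| Case | 7.1.2.6.3 read literally | 8.1 dating rule with Appendix 4 |
|---|---|---|
| Confirmed at 4-8 weeks | Event at first scan | Event at first scan |
| Resolved (reset) | Event at first scan | No event; process restarts |
| Persistent iUPD | Event at first scan | Provisional; rescan |
| Never rescanned | Event at first scan | Not addressed by the dating sentence |

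The readings agree on confirmed progression. They conflict outright on a reset.

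**4. One recoded patient.** Simulation with 200,000 trials, true one-year PFS 40% when every first progression counts, about 19.6 events expected. One observed event is moved later; the delay is an assumption.

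| Recoded event moved by | Favourable error, classical / averaged | One-year PFS |
|---|---|---|
| Not moved | 1.7 / 2.8% | 40.0% |
| 12 weeks | 1.9 / 3.2% | 40.5% |
| Median 3 months | 2.1 / 3.4% | 40.8% |
| Median 6 months | 2.6 / 4.1% | 41.5% |
| Median 12 months | 3.2 / 5.0% | 42.1% |

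**5. The opposite direction.** Suppose 40% and 65% were both set with resets not counted. Counting one reset, assumed at 0.12 to 0.60 years, gives one-year PFS of 65% × 24/25 = 62.4% and lowers classical power from about 83% to 77%.

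**6. Censoring.** Each lost patient credited with 12 unassessed weeks adds up to 0.916 × 12/52 = 0.21 expected events. Section 7.1.5.2 gives 12-week imaging after treatment stops for reasons other than progression; the 3-week gap and the loss rates are assumptions. Simulated one-year PFS, last visit against last scan:

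| Lost | 12-week gap | 3-week gap |
|---|---|---|
| 4% | 40.23 v 40.00% | 40.08 v 40.03% |
| 10% | 40.55 v 39.97% | 40.16 v 40.02% |
| 20% | 41.21 v 39.99% | 40.30 v 40.02% |

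In the worst cell, favourable error is 2.3% against 1.6% (classical) or 3.8% against 2.8% (averaged). Another model of when patients are lost, also with 20% lost, gives smaller gaps: 1.6% against 1.2%, and 2.8% against 2.2%.

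**The case against.** The best defence is that section 7.1.2.6.3 already sets the hierarchy. It names RECIST 1.1 as primary for the progression date, Appendix 4 presents iRECIST as a tool for managing participants, and the 8.1 rule also dates progression at the first scan. That favours counting every first progression, and the fix follows it. It does not close the point. If it governed alone, the confirmation condition in 8.1 would do no work, and 7.1.2.6.4 assigns iRECIST the assessment of progression as well as treatment decisions.

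Four stronger readings are tempting, and the documents do not support them.

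- **That progression never rescanned has no rule.** This is largely settled. Section 7.1.2.6.2 accepts progression without iRECIST ("due to documented disease progression and the Investigator elects not to implement iRECIST, this is the final required tumor imaging"), and 7.1.2.6.3 and the general PFS definition point to an event at the first scan. Persistent iUPD is mostly provisional, because a further scan is scheduled.
- **That the ambiguity favours the drug.** The direction depends on the criterion behind the 40%, which is not given.
- **That the error inflation is large.** If 20% of all PFS events were recoded with a 12-month median delay, error would be about 13.5 / 18.6%. That share is invented, and the pool includes deaths, which cannot reset. Limiting resets to the first six months, closer to the early flare described in 7.1.2.6.4, gives 4.7 / 7.2%.
- **That one recoded patient decides the induction objective.** It is true that 2/25 is 8% and 3/25 is 12%, either side of the hypothesised 10%. But section 8.2 plans only counts and percentages, with no test against 10%.

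On censoring, the plan does state a rule, so the criticism concerns the date chosen, and its effect is small.

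**Conclusion.** The point stands in a narrow form and should be fixed. For a progression that resets, the primary PFS event has two incompatible readings, and the documents do not choose between them. This rests on the text and needs no simulation.

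The size is illustrative. One recoded patient shifts one-year PFS by about 0.5 to 2 points, and in the classical test leaves favourable error at 1.9-3.2%, around the nominal 2.5%. These figures assume the cut-off, the delay and a truth in which every first progression counts. Neither the frequency of resets nor the net direction of bias can be derived from the documents. Last-visit censoring pushes PFS upward by about 0.1 to 1.2 points under the assumed losses and is minor.

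**What to change.** In section 8.1:

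1. Define the primary PFS event as death or the first RECIST 1.1 progression, dated at the first scan showing it, whether or not it is later confirmed. This agrees with 7.1.2.6.3 and also covers persistent iUPD and progression never rescanned.
2. Prespecify one sensitivity analysis in which a reset is not an event and any later progression is dated at its own first scan. Report the number of resets.
3. State the progression criterion behind the 40% benchmark.
4. Censor patients without an event at the last adequate tumor assessment, or at registration if there is none. Keep last-visit censoring as a sensitivity analysis.
5. Use the same progression rule for the descriptive induction-progression rate in section 8.2.

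Sections 7.1.2.6.1 (Tumor Imaging During the Study), 7.1.2.6.3 and 7.1.2.6.4 also differ on which criterion governs continuing or stopping treatment. They must be reconciled; no clinical rule is proposed here.

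The cost is a few lines of text and two sensitivity analyses. The PFS estimate would be slightly lower: by about 0.5 to 2 points for one reset patient in the illustration, and by about 0.1 to 1.2 points for censoring. If the benchmark did not count resets, some power is lost, for example from about 83% to 77% with one reset under the assumptions in step 5 of the working.
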